## 5.6 Sample size

Previous studies indicate a large effect size (Cohen's d 1.7). Therefore, for a size with 80% power and a 0.05 alpha, a sample size of 7 is required. We are proposing the conventional sample size of 30 patients for a feasibility study (10 participants per study arm). This will provide sufficient information to enable an accurate sample size calculation for use in a larger multicentre trial should a benefit be observed. If no benefit is seen to occur, then we can calculate the probability of having missed a potential benefit in our trial. This data will therefore inform the decision as to whether a future larger trial is warranted and necessary adjustments.

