# 4. Study design

## 4.1 Type of research

Prospective, randomised, single-centre, single blinded (observer) controlled trial of combination PDL and AFCO2L therapy to immature burn scars in adult patients with a burn scar between 1% and 5% total body surface area (TBSA), which meet inclusion criteria. This is a feasibility study to inform the development of a larger multi-centre RCT. In view of this, 10 patients will be recruited to each treatment arm and subsequent data analysis will reflect on wider RCT design and power.

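### Section 5.6 promises an accurate main-trial sample size if a benefit is observed, and a retrospective probability of a missed benefit if not; 10 per arm cannot support the first, and the second is a poor basis for the decision

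*Protocol*

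**What the plan says.** Protocol section 4.1 gives the purpose: "This is a feasibility study to inform the development of a larger multi-centre RCT". Section 5.6 starts from a Cohen's d of 1.7 taken from previous studies and states that "for a size with 80% power and a 0.05 alpha, a sample size of 7 is required". It then sets the actual size on other grounds: "We are proposing the conventional sample size of 30 patients for a feasibility study (10 participants per study arm").

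Two uses of the result follow, according to what is seen. If a benefit appears: "This will provide sufficient information to enable an accurate sample size calculation for use in a larger multicentre trial should a benefit be observed". If not: "If no benefit is seen to occur, then we can calculate the probability of having missed a potential benefit in our trial". The section closes: "This data will therefore inform the decision as to whether a future larger trial is warranted and necessary adjustments".

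Section 5.6 does not say what counts as an observed benefit, which outcome or which of the three pairwise comparisons is meant, whether the main trial would be sized from the observed effect or only from the SD, or at which effect the probability of a miss would be calculated. Section 7 sets p < 0.05 as the criterion of significance. Section 6 says that participants who withdraw are not replaced.

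**The concern.** The main product of a feasibility study is what it passes on to the next trial. Section 5.6 makes that depend on the effect seen in a small sample, in two ways.

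- **Benefit observed.** A sample size calculation is described as accurate, and it is tied to a favourable result. With 10 per arm both the SD and the effect are estimated loosely. Effects that pass a significance filter in a small trial also tend to be exaggerated.
- **No benefit seen.** A power statement made after a null result is offered as a measure of what may have been missed. Such a figure usually adds little to what is known beforehand, and it can reassure wrongly if it is calculated at an optimistic effect.

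At stake is a main trial that is too small after a lucky result, or an unlucky result that is given too much weight.

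**Working it through.** **Inputs from the protocol.** Section 5.6: d = 1.7, 80% power, alpha 0.05, stated n = 7, 10 per arm in three arms. **Assumptions of this check.** Two-sided tests, two-sample t-test on normal data, no dropout, and true effects d = 0.5, 0.8 and 1.2 as illustrations beside the protocol's 1.7.

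**1. The plan's own figure.** Two-sample t-test, two-sided 0.05, 80% power, d = 1.7: n = 6.55, so 7 per arm, with 83.1% power at 7. The stated 7 reproduces if it is read as per arm.

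**2. Precision of the SD.** Limits = SD × √(df/χ²), with df = 3 × (10 − 1) = 27.
- Lower: √(27/43.19) = 0.79. Upper: √(27/14.57) = 1.36.
- For a fixed raw difference N is proportional to SD², so N ranges from 27/43.19 = 0.63 to 27/14.57 = 1.85 times the estimate.
- With only two arms pooled (18 df) the limits are 0.76 to 1.48, and N ranges 0.57 to 2.19 fold.

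**3. Precision of a contrast.** Half-width = t(0.975; 18) × √(2/10) × SD = 2.101 × 0.447 = 0.94 SD. This is also the smallest observed d that can reach p < 0.05.

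**4. Sizing from the observed effect after a significant result.** 200,000 simulated 10 v 10 trials for each true d, keeping those significant in favour of laser. The main trial is sized at 80% power (noncentral t) from the median observed d among them.

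| True d | Significant | Median observed d | Planned per arm | Needed per arm | True power of main trial |
|---|---|---|---|---|---|
| 0.5 (assumed) | 18% | 1.16 | 13 | 64 | 23% |
| 0.8 (assumed) | 39% | 1.24 | 12 | 26 | 47% |
| 1.2 (assumed) | 72% | 1.40 | 10 | 12 | 72% |
| 1.7 (protocol) | 95% | 1.76 | 7 | 7 | 83% |

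If a benefit means only a favourable direction, planning from the observed d is still erratic. At an assumed true d of 0.5 the planned size has a 10th to 90th percentile range of 12 to 672 per arm (63 needed, both by the normal approximation).

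**5. Probability of having missed a benefit, three readings.**
- *At the observed effect.* With 10 per arm it is a function of p alone: p = 0.05 gives 51% power, p = 0.2 gives 24%, p = 0.5 gives 10%.
- *At a fixed standardised effect.* Miss probability = 1 − power at 10 per arm: 1 − 0.949 = 5% at d = 1.7, 1 − 0.395 = about 60% at 0.8, 1 − 0.185 = about 81% at 0.5. All are known before any patient is recruited.
- *At a fixed raw difference.* This does need the SD from the trial and inherits its imprecision. For a difference equal to one nominal SD, power at 10 per arm is 76% if the SD is 0.79 times nominal, 56% at nominal and 34% at 1.36 times nominal.

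**The case against.** The strongest reply is that section 5.6 does not commit to the methods criticised. It does not say that the main trial would be sized from the observed effect, that a benefit means p < 0.05, or that the missed-benefit probability uses the observed effect. A statistical analysis plan, not at hand here, could specify these. The text says that the data will inform the decision, not settle it, and asking what might have been missed suggests that a null result would not be taken at face value. At the only effect the protocol names, d = 1.7, the undersizing disappears.

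Much of this stands, and it limits the point. A reader might infer that section 5.6 sets a go/no-go rule that will mislead the next trial, that a worthwhile effect would usually be read as no benefit, or that the main trial would be badly undersized. The text supports none of these as fact: each depends on an unstated method or on an assumed true effect. A reader might also say that the missed-benefit calculation never needs data. That is true only for a fixed standardised effect.

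A reader might add that recruitment, retention and completeness are absent from the decision. That is an omission that could be filled elsewhere, not something section 5.6 states wrongly, and it is not part of this point.

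What the reply does not rescue is the word accurate, which fails even when only the SD is used, or the missed-benefit sentence, for which a confidence interval does better on every reading.

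**Conclusion.** The point holds in a limited form. The claim of an accurate sample size is not supported by 10 per arm: a 0.63 to 1.85 fold range in N at best (all arms pooled, nobody lost), and ±0.94 SD on any pairwise contrast. Unreplaced withdrawals would widen both.

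The missed-benefit probability restates p, or is already known, or rests on an imprecise SD, according to how it is calculated. It is a weak guide to whether a larger trial is warranted.

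Undersizing of the main trial is conditional. It arises if the observed effect is used after a significant result and the true effect is well below 1.7. It is severe at an assumed d of 0.5 or 0.8, modest at 1.2 and absent at 1.7. The figures assume normal data and two-sided t-tests. Section 5.6 is liable to mislead the planning of the next trial; it does not make that certain.

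**What to change.** In section 5.6:
- Delete the word accurate and the sentence on the probability of having missed a benefit.
- State that each pairwise contrast will be reported with its 95% CI and read against a clinically important difference fixed in advance.
- State that any main trial will be sized from that difference and the pooled SD, with allowance for the SD's uncertainty, not from the observed effect and not only if a benefit is observed. One convention among several is the upper one-sided 80% limit: √(27/20.70) = 1.14 × SD, hence 27/20.70 = 1.30 × N.

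Cost: rewording of one section and no added visits or measurements. The sponsor must choose and justify an important difference, which the protocol does not now give, and should expect a less favourable main-trial size.

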## 5.7 Follow-up duration

Following recruitment, patients will remain in the study for 8 months.

# 6. Consent

Consent to enter the trial must be sought from each participant only after a full explanation has been given, PIS provided, and time allowed for consideration and any questions they may have. Written participant consent will be obtained. If a participant is willing to enrol, but physically unable to sign an ICF (for example, burns to hands), there will be an option for witnessed verbal consent. This will be witnessed by a healthcare professional unrelated to the study. The right of the participant to refuse to participate without giving reasons will be respected. Participants are allowed to withdraw at any stage of the study without compromising their care in the hospital. Data already collected will be retained for use in the study, but patients will not be replaced if they withdraw from the project.

Written versions of the PIS and ICF will be presented to the participants detailing no less than:

- the exact nature of the trial;
- what it will involve for the participant;
- the implications and constraints of the protocol;
- the known side effects and any risks involved in taking part.

It will be clearly stated that the participant is free to withdraw from the trial at any time for any reason without prejudice to future care, without affecting their legal rights, and with no obligation to give the reason for withdrawal. The participant will be allowed one week to consider the information, and the opportunity to question the Investigator whether to decide whether they will participate in the trial.

Written informed consent will then be obtained by means of the approved ICF. The person who obtains consent must be suitably qualified and experienced, hold a valid GCP certificate and have been delegated to do so by the CI. A copy of the signed ICF will be given to the participant. The original signed form will be retained in the trial site file, with a copy added to the participants' medical notes, along with a copy of the PIS.

## 6.1 Participant Confidentiality

The PI must ensure that a participant's anonymity will be respected throughout the study and that their identities are protected from unauthorized parties. A participant's privacy and confidentiality will be maintained by the assignment of a unique identification number. The Investigator will keep a participant log showing codes and names of the participants. Confidentiality and protection of data will be maintained according to local regulatory requirements.

# 7. Statistical methods

Descriptive, univariate statistics will be used to describe the general characteristics of the sample. Differences between "Control" and "Intervention" groups will be examined using the Wilcoxon Signed Rank test, and a p value < 0.05 will be considered to indicate statistical significance. All statistical analysis will be conducted using PRISM.

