# **Trial Summary**

| Name and Designation   |
|--|
| Chief Investigator (CI): [name], Consultant Burn Surgeon, Royal |
| Victoria Infirmary, Newcastle upon Tyne  |
| Co-investigator: [name], Clinical Psychologist, Royal Victoria    |
| Infirmary, Newcastle upon Tyne   |
| Research Team Lead: [name]  |
| Freeman Hospital, Newcastle upon Tyne  |
| Sponsor: The Newcastle upon Tyne Hospitals NHS Foundation Trust                |
|  |

| Trial Title          | A feasibility study assessing combined pulsed dye and fractional CO 2 laser |  |  |
|----------------------|--|--|--|
|                      | on burn scar outcomes versus standard care   |  |  |
| short title          | CLIPSO (Combined Laser Improves Scar Outcome)  |  |  |
| Clinical Phase       | N.A.   |  |  |
| Trial Design         | Randomized controlled single, blinded study  |  |  |
| Trial Participants   | Adults with hypertrophic burn scars  |  |  |
| Sample Size          | 10 to each treatment arm   |  |  |
| Intervention         | Combination pulsed dye and fractional CO 2 laser versus standard care       |  |  |
| Follow up duration   | 8 months   |  |  |
| Planned Trial Period | 24 months  |  |  |
| Objectives           |  |  |  |
| Primary              | To determine if combined pulsed dye and fractional CO 2 laser treatment     |  |  |
|                      | versus fractional CO 2 laser alone or standard scar therapy improves        |  |  |
|                      | patient and observer reported scar appearance.   |  |  |
| Secondary            | To determine if combined laser treatment versus AFCO 2 L alone              |  |  |
|                      | standard scar therapy on burn scars improves patient reported symptoms                 |  |  |
|                      | of itch and psychological sequelae.  |  |  |
|                      |  |  |  |

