# 3. Project Aim, Objectives & Hypothesis

## 3.1 Aim

To investigate if the early use of combination laser treatment helps minimise scar, improves patient satisfaction with scar appearance and associated symptoms versus single AFCO2L treatment or standard care alone.

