## 4.2 Inclusion Criteria

- Participants > 18 years of age
- Hypertrophic burn scar ≥1% and 5% TBSA
- Scars which would ordinarily be managed by pressure garments and laser intervention
- All patients to be less than 3 months from discharge at point of recruitment.

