## 5. Methods

All adult patients treated at the Royal Victoria Infirmary Northern Regional Burn Centre will be screened for admission. Those patients who meet the selection criteria will be informed about the study and asked to participate at their six-week clinic appointment.

Each patient will be randomised to one of three groups: COMBINED LASER (CL), SINGLE LASER (SL) or CONTROL (C) group. A single hypertrophic scar site >1% -5% TBSA is required for each patient. This scar size is deemed appropriate for topical local anaesthesia laser treatment as an outpatient.

[figure not shown]
In the event that the patient has multiple or large areas of hypertrophic scar, study participation will only be offered if laser treatment under topical local anaesthesia is possible and if the study participant consents to this. If the study PI feels this is not feasible, study participation will not be offered and the patient will continue with standard of care as provided by the host unit.

The rationale for this is that it is unethical to treat an area of hypertrophic scar within a large scar burden as standard of care in our host institution would be to treat all areas with AFCO2L if deemed a suitable candidate. Furthermore, previous experience has illustrated that the subjective nature of PROMs makes it difficult for participants to provide meaningful answers if a small area of scar has been treated within a large scar volume; it is not possible to selectively comment on the daily physical/psychological impact of a small treated area if most of a limb/body is scarred.

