# 5.3 Maintenance of any blinding records or randomisation codes and procedures for breaking codes

The Sealed Envelope online software (www.sealedenvelope.com) will be used to randomly allocate study participants to combined laser (CL), single laser (SL) or control (C) groups. The PI will select the scar and the anatomical location of the scar, and the site name (CONTROL, COMBINED LASER or SINGLE LASER) will be recorded immediately on a spread sheet. The area will be marked and photographed prior to treatment and following patient consent for medical photography images. There is no foreseen scenario whereby the laser site or the control site will be required to change. As this is a single blinded study, participants will know which treatment arm they are in negating the necessity to break blinding.

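### Section 7 specifies only a Control versus Intervention comparison, with Intervention undefined, so the protocol's analysis leaves out combined laser versus AFCO2 laser alone, one of the two comparisons in the primary objective

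*Protocol*

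**What the plan says.** **Design.** Protocol section 5 (Methods) states: "Each patient will be randomised to one of three groups: COMBINED LASER (CL), SINGLE LASER (SL) or CONTROL (C) group". Section 5.3 repeats that the software will "randomly allocate study participants to combined laser (CL), single laser (SL) or control (C) groups". Section 5.6 plans 30 patients, 10 per arm.

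**Question.** The primary objective in the Trial Summary table asks whether combined treatment "versus fractional CO 2 laser alone or standard scar therapy improves" scar appearance as reported by patient and observer. Section 3.1 sets the combination "versus single AFCO 2 L treatment or standard care alone". Section 3.2 carries the same two comparators into both objectives.

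**Analysis.** Section 7 gives one between-group analysis: "Differences between 'Control' and 'Intervention' groups will be examined", by the Wilcoxon signed-rank test, with p below 0.05 as the criterion. Nowhere does the protocol define the intervention group, describe a three-group analysis or specify CL against SL.

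**The concern.** Two comparators are named in the objective and three arms are randomised, but the analysis has room for two groups. The SL arm has one purpose that no other arm can serve: it shows what pulsed dye laser adds to AFCO2 laser. That needs CL against SL.

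If the laser arms are pooled, the result answers whether any laser regimen differs from scar therapy without laser. A benefit due entirely to AFCO2 laser could then be read as support for the hypothesis in section 3.3, which is about combined treatment. Section 1 also says the study should show whether treatment streams can be refined for the larger trial, and a comparison with control alone does not show whether the combined stream is worth carrying forward. If the contrast is chosen only once data are in hand, the choice can be influenced by the results.

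**Working it through.** **1. What the intervention group could mean**

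| Reading | Support in the protocol | Contrast obtained | CL versus SL? |
|---|---|---|---|
| CL and SL pooled | Section 5.1 counts both laser groups as treatment-arm patients; section 5.2 contrasts control with treatment arm | Any laser v C, 20 v 10 | No |
| CL only | The trial title and the Intervention row of the Trial Summary table name only the combination against standard care | CL v C, 10 v 10 | No |
| Each laser arm separately against control | Section 1 on refining treatment streams | CL v C and SL v C | No |

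Pooling is the likeliest reading. The gap is the same under all three.

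**2. The protocol's own figure**

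Section 5.6 gives Cohen's d = 1.7, 80% power, alpha 0.05 and a required size of 7. It does not state the contrast, the sidedness, or whether 7 is per group. Assume a two-sided t-test of two independent groups, with noncentrality d / √(1/n₁ + 1/n₂):

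- Solving for 80% power gives n = 6.55, so 7 per group.
- At n = 7 the noncentrality is 1.7 / √(2/7) = 3.18, and power is 83.1%. At n = 6 power is 75.6%.
- With the large-sample rank-test efficiency of 0.955, 6.55 / 0.955 = 6.86, again 7 per group.

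The stated 7 therefore fits one comparison of two independent arms. The objective needs two.

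**3. What a pooled test shows**

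With equal arms, the pooled contrast estimates the average of the two effects against control, (CL−C + SL−C) / 2. The same average arises whether CL is better than, equal to or worse than SL.

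For 20 v 10, √(1/20 + 1/10) = 0.387. The effect detectable with 80% power at two-sided 0.05 is d = 1.12 (noncentrality 1.12 / 0.387 ≈ 2.9, 28 degrees of freedom). If CL and SL both have d = 1.12 against control, the pooled test has 80% power while the true CL-SL difference is zero. The value 1.12 is an assumption for illustration; the protocol's only effect size is 1.7, at which the pooled test has 98.9% power.

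**4. What CL versus SL can show at 10 v 10**

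- 95% CI half-width: t(0.975, 18 df) × √(1/10 + 1/10) = 2.101 × 0.447 = 0.94 SD.
- Half-width for the pooled 20 v 10 contrast: 2.048 × 0.387 = 0.79 SD.
- Effect detectable with 80% power, two-sided 0.05: d = 1.32.

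| Assumed CL-SL effect (d) | Power at 10 v 10 |
|---|---|
| 0.5 | 19% |
| 0.8 | 40% |
| 1.0 | 56% |
| 1.7 | 95% |

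The protocol gives no expected effect for CL versus SL, so the effects in this table are assumptions. The figures also assume all 10 per arm are analysed; section 6 says withdrawals are not replaced, so precision may be lower.

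**The case against.** The strongest reply is that section 7 is a brief statement in a 30-patient feasibility protocol. It never mentions pooling, and a separate SAP may define the groups and add the contrast. That stands in part: it would go too far to say that CL versus SL will never be estimated, or that pooling is certain. It does not remove the conflict, because the protocol fixes a comparison that differs from its own objective, and an SAP should elaborate that analysis rather than replace it.

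It may also be said that the pooled-power figure is true by construction and uses a t-test where section 7 names a Wilcoxon test. Both are fair. The figure only illustrates how easily a positive pooled result could arise without any benefit from the added laser.

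Two stronger readings are tempting but not supported:

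- **Error inflation.** A reader might infer that every scale and visit will be tested at 0.05 and quote a family-wise error rate. Section 7 does not say this. With the single contrast as written, four scales (POSAS patient, POSAS observer, MSS, BBSIP) at two visits make 4 × 2 × 1 = 8 tests, and 1 − 0.95⁸ is about 34% if they were independent, which they are not. Naming a primary visit and a multiplicity rule is commonly left to the SAP, and formal ordered testing is debatable in a feasibility study.
- **Wrong comparator.** A reader might infer that the control arm is not the host unit's standard care. Section 4.2 gives some support, since it requires "Scars which would ordinarily be managed by pressure garments and laser intervention", but it does not say when laser would be given. The sentence in section 5 that "standard of care in our host institution would be to treat all areas with" AFCO2 laser concerns patients with a large scar burden and is limited to suitable candidates. Section 5.1 describes standard scar therapy without laser. These passages need reconciling, which is a separate and minor matter.

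**Conclusion.** The point holds and should be corrected. As written, the protocol's analysis omits one of the two comparisons in its primary objective under each plausible reading of the intervention group. Under the likeliest reading, a positive result at the usual power needs only an average laser effect of about 1.12 SD and says nothing about the combination over AFCO2 laser alone.

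The omission rests on the text and needs no numerical assumption. The sizes assume t-tests, equal variances, two-sided 0.05 and full follow-up. CL versus SL will be imprecise in this trial (about ±0.94 SD; 80% power only from d of about 1.32), so it should inform the larger trial and not be presented as a definitive test.

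**What to change.** In section 7:

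1. Define the groups as a three-level arm factor (CL, SL, C) and state that the laser arms are not pooled.
2. Name the contrasts CL-C and CL-SL, with SL-C as supportive, and report each as an estimate with a 95% CI.
3. Use a method for independent groups. The signed-rank test named there is for paired data, and patients in different arms are not pairs.
4. State the expected precision of CL-SL at 10 v 10 and that it serves to plan the larger trial.

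Separately, reconcile sections 4.2, 5 and 5.1 on whether scar therapy without laser is what the protocol means by standard care, and label the control arm to match.

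The cost is a change of wording, with no extra patients, visits or data. The downside is small: each 10 v 10 contrast is less precise than the pooled one (about ±0.94 against ±0.79 SD).

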Participants will be divided into three groups: control, AFCO2L only and combined PDL and AFCO2L treatment. Both laser groups will receive 3 treatments 6 weeks apart. Outcome measures will be conducted before laser treatment, 6 weeks after the last treatment of laser and 3 months post laser treatment. This feasibility study will serve to inform a larger multi-centre RCT in terms of study power, outcome measure frequency and whether treatment streams can be refined.

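### Section 7 compares independent randomised arms with the Wilcoxon signed-rank test, a paired test, so its p-value would rest on an arbitrary pairing of unrelated patients or could not be computed

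*Protocol*

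**What the plan says.** Protocol section 7 gives one inferential method. It states "Differences between 'Control' and 'Intervention' groups will be examined" and names the test in the same sentence: the "groups will be examined using the Wilcoxon Signed Rank test", with p < 0.05 as the threshold. It does not say whether Intervention means the two laser arms pooled or each one separately.

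The design sections describe independent groups:

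- Section 5: "Each patient will be randomised to one of three groups: COMBINED LASER (CL), SINGLE LASER (SL) or CONTROL (C) group".
- Section 5, on what each patient contributes: "A single hypertrophic scar site >1% -5% TBSA is required for each patient".
- Section 5.3: online software "will be used to randomly allocate study participants to combined laser (CL), single laser (SL) or control (C) groups".

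No section describes matching patients across arms. Section 5.3 also contains the sentence "There is no foreseen scenario whereby the laser site or the control site will be required to change".

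Section 5.6 plans 30 patients, 10 per arm, and quotes a required size of 7 for d = 1.7, 80% power and alpha 0.05. Section 6 says that withdrawn patients are not replaced and that data already collected are kept.

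**The concern.** The signed-rank test ranks the differences within pairs. It needs a rule, fixed by the design, that says which control value belongs with which intervention value. Here no patient supplies both. The contralateral colorimeter reading in section 5.5 is no substitute: it comes from unscarred skin and is not a Control-arm outcome.

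This matters because section 7 names no other test, and section 5.6 ties the decision on a larger trial to whether a benefit is observed. A p-value that changes with the order of rows in a spreadsheet is a poor basis for that decision. With no pairing rule in the protocol, the pairing could also be chosen after the data are seen.

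**Working it through.** **Inputs.** From the protocol: three arms of 10, one scar per patient, no matching, d = 1.7, 80% power, alpha 0.05, no replacement of withdrawals. Assumptions, not in the protocol: normal outcomes with equal variance, two-sided tests, and a smaller effect of d = 1.0 (a shift of about 1 SD) to illustrate less clear-cut data.

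**1. The plan's own figure.** For two independent groups the normal approximation is n per arm = 2(1.96 + 0.842)²/1.7² = 15.70/2.89 = 5.4, so 6. The two-sided two-sample t-test gives 6.55, so 7 per arm, with power 83.1% at 7. This reproduces the stated 7. A paired t-test gives 4.94, so 5 pairs, or 5.18, so 6 pairs, after dividing by a rank-test efficiency of 0.955. The figure matches an independent-groups calculation exactly, although section 5.6 does not say which formula was used.

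**2. What the named test would do.** With controls x and intervention values y, the signed-rank statistic uses D_i = y_i − x_i. The design supplies no link between the i-th control and the i-th intervention patient. With 10 v 10 there are 10! = 3,628,800 possible pairings, and none has priority. The rank-sum test uses only the pooled ranks, so it gives one p-value.

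**3. One fixed data set, many pairings.** Take 10 normal quantiles for control and the same values shifted by about 1 SD for intervention.

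| Test | p-value |
|---|---|
| Rank-sum | 0.043 |
| Signed-rank, 5,000 random pairings | 0.002 to 0.375, median 0.064 |
| Signed-rank, 5th to 95th percentile | 0.010 to 0.160 |
| Share of pairings with p < 0.05 | 46% |

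The lower end, 0.002, is the smallest two-sided p that 10 pairs can give (2/2¹⁰ = 2/1024). This data set is borderline by construction, so it shows that the verdict can flip, not how often it does.

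**4. How often it matters.** Simulated 10 v 10 data, not selected on the p-value, with one random pairing fixed in advance:

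| True d | Same verdict as rank-sum | Rejection: signed-rank v rank-sum |
|---|---|---|
| 0 | about 97% | signed-rank about 5% |
| 1.0 | about 85% | about 50% v 51% |
| 1.7 | about 95% | about 91–92% v 93% |

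The 5% can be confirmed exactly. With 10 pairs the two-sided test at 0.05 rejects when the smaller rank sum is 8 or less. There are 25 sign patterns in each tail, so the level is 50/1024 = 4.9%.

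At d = 1.7 only about 11% of data sets had a rank-sum p between 0.02 and 0.08. In about 21% the verdict still varied materially with the pairing (between 5% and 95% of pairings significant).

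**5. Unequal arms.** If Intervention pools both laser arms, the comparison is 10 + 10 = 20 v 10, and 10 laser patients have no partner. A trial run on samples of 10 and 20 stopped with an error. Any imbalance from withdrawal has the same effect: with 10 v 9, one patient must be dropped.

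**6. After the fix.** Simulated rank-sum power at d = 1.7, two-sided 0.05 for a single contrast: about 77% at 7 v 7, 93% at 10 v 10 and 98% at 10 v 20.

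**The case against.** The strongest reply is that signed-rank is a slip for rank-sum. The stated 7 fits an independent-groups formula, the study is a feasibility trial, and an analysis plan may put it right. All of that is possible. It does not change what section 7 says: this is a wrong statement rather than a detail left for later, and an analysis plan could mend it only by contradicting the protocol.

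Several stronger readings are tempting, and the documents do not support them:

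- *The test inflates false positives, or the verdict generally follows row order.* It does not. With a pairing fixed in advance the level stays at or below 5%, and at the protocol's own d = 1.7 the loss of power is small. Dramatic swings come from borderline data.
- *Any withdrawal makes the test impossible.* Equal losses leave equal arms. Because section 6 keeps data already collected, a withdrawal after month 4 need not affect the month-4 comparison. Withdrawals can cause the problem but need not.
- *A before-versus-after version would credit natural scar maturation to laser.* Section 7 describes a comparison between groups, so this is hypothetical. The control arm is also measured over time.
- *Section 5.3 shows a leftover within-patient design.* In 5.3 the site name is the label given to each patient's scar, so the laser site and the control site can belong to different patients. The wording is loose, but it is not evidence of pairing or of an abandoned design.

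**Conclusion.** The point stands. The only inferential test in the protocol is a paired test, and the design has no pairs. The result would be a p-value that is not unique or, with unequal groups, one that cannot be obtained without discarding patients.

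The size is moderate. On the simulations an arbitrary pairing fixed in advance would change the verdict in about 5% of trials at d = 1.7 and about 15% at d = 1.0, without raising type I error. The exposure is greatest for borderline results and where the pairing is not fixed before the data are seen, and the protocol fixes none. These rates assume normal outcomes with equal variance and 10 complete patients per arm. The mismatch between test and design depends on none of those assumptions. It should be corrected before analysis.

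**What to change.** In section 7, replace the signed-rank test with the Wilcoxon rank-sum (Mann-Whitney) test for each named pair of arms: combined laser v control, and combined laser v single laser, which are the contrasts in the objectives. Another method for independent groups, such as a model with arm as a three-level factor, would serve equally well. The rank-sum test is the smallest change, since the protocol already chose a rank test.

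In the same edit, state whether Intervention means each laser arm separately or both pooled. This decides whether the comparison is 10 v 10 or 20 v 10.

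Clarifying the site wording in section 5.3 is optional. The cost is a sentence or two in section 7, with no change to visits, data collection or sample size.
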